## 7 SELECTION OF PATIENTS

### 7.1 INCLUSION CRITERIA

- I 01. Adults and adolescent patients with a physician diagnosis of asthma for  $\geq 12$  months, based on the Global Initiative for Asthma (GINA) 2014 Guidelines and the following criteria:
- A) Existing treatment with medium to high dose ICS ( $\geq 250$  mcg of fluticasone propionate twice daily or equipotent ICS daily dosage to a maximum of 2000 mcg/day of fluticasone propionate or equivalent) in combination with a second controller (eg, LABA, LTRA) for at least 3 months with a stable dose  $\geq 1$  month prior to Visit 1.
    - Note for Japan: for subjects aged 18 years and older, ICS must be on  $\geq 200$  mcg of fluticasone propionate twice daily or equivalent; for subjects aged 12 to 17 years, ICS must be  $\geq 100$  mcg of fluticasone propionate twice daily or equivalent.
    - Patients requiring a third controller for their asthma will be considered eligible for this study, and it should also be used for at least 3 months with a stable dose  $\geq 1$  month prior to Visit 1.
  - B) Pre-bronchodilator forced expiratory volume ( $FEV_1$ )  $\leq 80\%$  of predicted normal for adults and  $\leq 90\%$  of predicted normal for adolescents at Visits 1 and 2, prior to randomization.
  - C) Asthma Control Questionnaire 5-question version (ACQ-5) score  $\geq 1.5$  at Visits 1 and 2, prior to randomization.
  - D) Reversibility of at least 12% and 200 mL in  $FEV_1$  after the administration of 200 to 400 mcg albuterol/salbutamol or levalbuterol/levosalbutamol (2 to 4 inhalations of albuterol/salbutamol or levalbuterol/levosalbutamol, or of a nebulized solution of albuterol/salbutamol or levalbuterol/levosalbutamol, if considered as a standard office practice) before randomization.
  - E) Must have experienced, within 1 year prior to Visit 1, any of the following events:
    - Treatment with a systemic steroid (oral or parenteral) for worsening asthma at least once.
    - Hospitalization or emergency medical care visit for worsening asthma.
- I 02. Signed written informed consent.

### 7.2 EXCLUSION CRITERIA

Patients who have met all the above inclusion criteria listed in Section 7.1 will be screened for the following exclusion criteria which are sorted and numbered in the following 4 subsections:

### 7.2.1 Exclusion criteria related to study methodology

- E 01. Patients <12 years of age or the minimum legal age for adolescents in the country of the investigative site, whichever is higher (For those countries where local regulations permit enrollment of adults only, subject recruitment will be restricted to those who are  $\geq 18$  years of age).
- E 02. Weight is less than 30 kilograms.
- E 03. Chronic obstructive pulmonary disease (COPD) or other lung diseases (eg, idiopathic pulmonary fibrosis, Churg-Strauss Syndrome, etc) which may impair lung function.
- E 04. A subject who experiences a severe asthma exacerbation (defined as a deterioration of asthma that results in emergency treatment, hospitalization due to asthma, or treatment with systemic steroids at any time from 1 month prior to the Screening Visit up to and including the Baseline Visit).
- E 05. Evidence of lung disease(s) other than asthma, either clinical evidence or imaging (Chest X-ray, CT, MRI) within 12 months of Visit 1 or at the screening visit, as per local standard of care.  
  
Note for Japan: According to the request from the health authority, chest X-ray should be performed at screening visit if there is no chest imaging (Chest X-ray, CT, MRI) available within 3 months prior to screening to exclude patients with suspected active or untreated latent tuberculosis.
- E 06. A subject who has experienced an upper or lower respiratory tract infection within the 4 weeks prior to Visit 1 or during the screening period.
- E 07. Current smoker or cessation of smoking within 6 months prior to Visit 1.
- E 08. Previous smoker with a smoking history  $>10$  pack-years.
- E 09. Comorbid disease that might interfere with the evaluation of IMP.
- E 10. Known or suspected alcohol and/or drug abuse.
- E 11. Inability to follow the procedures of the study (eg, due to language problems or psychological disorders).
- E 12. Patients requiring non-selective beta-1 adrenergic receptor blockers for any reason, or initiation or change in dose of a selective beta-1 adrenergic receptor blocker within 1 month prior to Visit 1 or plan to initiate or change in dose of a selective beta-1 adrenergic receptor blocker during the screening period or the randomized treatment period.
- E 13. Anti-immunoglobulin E (IgE) therapy (omalizumab) within 130 days prior to Visit 1 or any other biologic therapy/immunosuppressant to treat inflammatory disease or autoimmune disease (eg, rheumatoid arthritis, inflammatory bowel disease, primary biliary

cirrhosis, systemic lupus erythematosus, multiple sclerosis, etc.) as well as other diseases within 2 months or 5 half-lives prior to Visit 1, whichever is longer.

- E 14. Initiation of allergen immunotherapy within 3 months prior to Visit 1 or dose change from 1 month prior to Visit 1 or a plan to begin allergen immunotherapy or to change its dose during the Screening Period or the Randomized Treatment Period.
- E 15. Patients on or initiation of Bronchial thermoplasty within 3 years prior to Visit 1 or plan to begin therapy during the Screening Period or the Randomized Treatment Period.
- E 16. Exposure to another investigative antibody within a time period prior to Visit 1 that is less than 5 half-lives of the antibody. In case the half-life is not known, then the minimum interval since exposure to the prior investigative antibody is 6 months. The minimum interval since exposure to any other (non-antibody) investigative study medication is 30 days prior to Visit 1.
- E 17. Patients receiving medications or therapy that are prohibited as concomitant medications (See Section 8.8).
- E 18. Patients who have previously been treated in any clinical trial of dupilumab.
- E 19. Patient is the Investigator or any Sub-Investigator, research assistant, pharmacist, study coordinator, other staff or relative thereof directly involved in the conduct of the study.

#### **7.2.2 Exclusion criteria related to the active comparator and/or mandatory background therapies**

- E 20. Non-compliance with use of the mandatory background therapy, eg, ICS/LABA combination, during the screening period, as defined as:
  - <80% of total number of prescribed doses of background medication taken during the screening period. Compliance is verified based on background medication use recorded on the patient electronic diary during the screening period.
- E 21. A subject with a history of clinically significant renal, hepatic, cardiovascular, metabolic, neurologic, hematologic, ophthalmologic, respiratory, gastrointestinal, cerebrovascular or other significant medical illness or disorder which, in the judgment of the investigator, could interfere with the study or require treatment that might interfere with the study. Specific examples include but are not limited to uncontrolled diabetes, uncontrolled hypertension, bronchiectasis. Active tuberculosis or non-tuberculous mycobacterial infection, latent untreated tuberculosis or a history of incompletely treated tuberculosis will be excluded from the study unless it is well documented by a specialist that the patient has been adequately treated and can now start treatment with a biologic agent, in the medical judgment of the investigator and/or infectious disease specialist. Tuberculosis testing would be performed on a country by country basis according to local guidelines if required by regulatory authorities or ethic committees. Other conditions that are well controlled and stable will not prohibit participation if deemed appropriate per the investigator's judgment.

### 7.2.3 Exclusion criteria related to the current knowledge of Sanofi compound

E 22. Pregnant or breast-feeding women.

E 23. Women of childbearing potential (pre-menopausal female biologically capable of becoming pregnant) who:

- Do not have a confirmed negative serum beta-hCG test at Visit 1.
- Who are not protected by one of the following acceptable forms of effective contraception during the study:
  - Established use of oral, injected, implanted or inserted hormonal contraceptive.
  - Intrauterine device (IUD) with copper or intrauterine system (IUS) with progestogen
  - Barrier contraceptive (condom, diaphragm or cervical/vault caps) used with spermicide (foam, gel, film, cream or suppository), if allowed by local regulation
  - Female sterilization (eg tubal occlusion, hysterectomy or bilateral salpingectomy),
  - Male sterilization with post-vasectomy documentation of the absence of sperm in the ejaculate; for female patients the study, the vasectomized male partner should be the sole partner for that patient
  - True abstinence in keeping with the preferred and usual lifestyle and if allowed by local regulation; periodic abstinence (eg calendar, ovulation, symptothermal, post-ovulation methods) is not an acceptable method of contraception
  - Postmenopausal women (defined as at least 12 consecutive months without menses) are not required to use additional contraception

E 24. Deleted.

E 25. Diagnosed active parasitic infection (helminthes), suspected or high risk of parasitic infection, unless clinical and (if necessary) laboratory assessments have ruled out active infection before randomization.

E 26. History of HIV infection or positive HIV serology at Visit 1.

E 27. Known or suspected history of immunosuppression, including history of invasive opportunistic infections (eg, histoplasmosis, listeriosis, coccidioidomycosis, pneumocystosis, aspergillosis), despite infection resolution; or unusually frequent, recurrent or prolonged infections, per investigator's judgment.

E 28. Evidence of acute or chronic infection requiring systemic treatment with antibacterials, antivirals, antifungals, antiparasitics, or antiprotozoals within 4 weeks before Visit 1 or during the screening period, significant viral infections within 4 weeks before Visit 1 or during the screening period that may not have received antiviral treatment (eg, influenza receiving only symptomatic treatment).

- E 29. Live attenuated vaccinations within 4 weeks prior to Visit 1 or planned live attenuated vaccinations during the study; see Appendix A for list of prohibited live attenuated vaccines.
- E 30. Patients with active autoimmune disease or patients using immunosuppressive therapy for autoimmune disease (eg, rheumatoid arthritis, inflammatory bowel disease, primary biliary cirrhosis, systemic lupus erythematosus, multiple sclerosis, etc.) or patients with high titer autoantibodies at screening who are suspected of having high risk for developing autoimmune disease at the discretion of the Investigator or the Sponsor.
- E 31. History of malignancy within 5 years before the screening visit, except completely treated in situ carcinoma of the cervix, completely treated and resolved nonmetastatic squamous or basal cell carcinoma of the skin.
- E 32. Patients with a history of a systemic hypersensitivity reaction, other than localized injection site reaction, to any biologic drug.
- E 33. Patients with any of the following result at screening:
- Positive (or indeterminate) HBs Ag or,
  - Positive IgM HBc Ab or
  - Positive total HBc Ab confirmed by positive HBV DNA or
  - Positive HCV Ab confirmed by positive HCV RNA
- E 34. Liver injury related criteria:
- Clinically significant/active hepatobiliary disease or
  - Alanine Aminotransferase (ALT) >3 Upper Limit of Normal (ULN)
- E 35. Abnormal lab values at Screening:
- Creatine phosphokinase (CPK) >10 ULN or
  - Platelets <100,000 cells/mm^3 or
  - Eosinophils >1500 cells/mm^3

#### **7.2.4 Additional exclusion criteria during or at the end of screening**

- E 36. Patient who has withdrawn consent before enrollment/randomization.

## **8 STUDY TREATMENTS**

### **8.1 INVESTIGATIONAL MEDICINAL PRODUCT(S)**

#### **8.1.1 Dupilumab**

Sterile dupilumab of various concentrations will be provided in 150 mg/mL in glass pre-filled syringe to deliver 300 mg in 2 mL and 175 mg/mL in glass pre-filled syringe to deliver 200 mg in 1.14 mL.

#### **8.1.2 Placebo**

Sterile placebo for dupilumab will be provided in identically matched glass pre-filled syringe to deliver 2 mL or 1.14 mL, which will match dupilumab 300 mg (2 mL) and 200 mg (1.14 mL) respectively.

#### **8.1.3 Preparation of investigational product**

Dupilumab or matching placebo in glass pre-filled syringes will be dispensed to the patients.

#### **8.1.4 Dosing schedule**

Two injections of IMP will be administered on Day 1 at Visit 2 as a loading dose. Subsequently one injection of IMP will be given every  $14 \pm 3$  days (q2w). The doses of investigational product must be separated by  $\geq 11$  days to avoid an overdose.

The Investigator or delegate will train the patient (or caregiver(s)) how to prepare and inject IMP at Visit 2 and will inject the first of the 2 injections. The patient (or caregiver(s)) will perform the second injection under the supervision of the Investigator or delegate. This training must be documented in the patient's study file. At subsequent study visits, patients are trained to self-inject IMP, and the patients are allowed to self-inject IMP at home after 6 injections at investigational site, counting from Visit 3.

Patients should be instructed to avoid missing any doses of medication during the study. Any patient who misses one dose should be reminded to be diligent, in order to avoid further missing doses thereafter. In case of missed dose(s) no loading dose of 2 injections will be administered when restarting the treatment, whatever the number of missed doses. The patients should continue on their scheduled IMP treatment and visit, even if more than 2 consecutive doses are missed.

When the patient has a study visit, the IMP will be administered following clinic procedures and blood collection. Patients should be monitored for at least 30 minutes after each study-site administered investigational product administration for any signs or symptoms of a hypersensitivity reaction.

For doses not given at the study site, diaries will be provided to record information related to the injections. The diary will be kept as source data in the patient's study file.

If the patient (or caregiver) is unable or unwilling to administer IMP, arrangements must be made for qualified site personnel and/or health care professionals (eg, visiting nurse service) to administer IMP for the doses that are not scheduled to be given at the study site.

If the study visit is not performed at the site as scheduled, the dose will be administered by the patient and/or their caregiver/health care professional, or arrangements must be made for an unscheduled visit at the site to administer the IMP. When IMP is administered at home, the patients must be advised by the site staff to self-monitor for potential signs and symptoms that may suggest a hypersensitivity reaction for at least 30 minutes after administration.

If the patient, or caregiver(s) do not develop the comfort to inject the investigational drug at home, or the Investigator determines that patient (or caregiver) injection at home is not appropriate, injections can be performed at the site by way of unscheduled visits.

Subcutaneous injection sites should be alternated among the 4 quadrants of the abdomen (avoiding navel and waist areas), the upper thighs or the upper arms, so that the same site is not injected twice consecutively. Injection in the upper arms could be done only by a trained person (Parent/ caregiver trained by Investigator or Delegate) or health care professional but not the patient themselves. This instruction pertains to the day that the loading dose is injected as well as the administration of q2w injections. For each injection, the anatomic site of administration will be recorded in the electronic case report form (e-CRF) and, as applicable, the home diary.

Detailed instructions for transport, storage, preparation, and administration of IMP are provided to the patient. Patients will complete a dosing diary to document compliance with self-injection (or caregiver) injection of IMP.

## **8.2 NONINVESTIGATIONAL MEDICINAL PRODUCT(S)**

### **8.2.1 Inhaled corticosteroid in combination with one or two other controllers**

On a daily basis throughout the study, the patient uses an electronic diary to record daily use of ICS in combination with other controllers as used just prior to screening. The controller drugs will not be dispensed or supplied by the sponsor.

The recognized asthma controllers for the study will include the following 5 classes: ICS, LABA, LAMA, Anti-leukotrienes and methylxanthines. Please refer to Appendix O for a list of commonly used asthma controller medication.

#### **8.2.1.1 Screening period**

Prior to screening, patients must be on a stable background therapy of a medium to high dose of ICS ( $\geq 250$  mcg of fluticasone propionate twice daily or equipotent ICS daily dosage to a maximum of 2000 mcg/day of fluticasone propionate or equivalent) [Note for Japan: subjects

aged 18 years and older, ICS must be  $\geq 200$  mcg of fluticasone propionate twice daily or equivalent; subjects aged 12 to 17 years, ICS must be  $\geq 100$  mcg of fluticasone propionate twice daily or equivalent] in combination with a second controller medication (Refer to Appendix O on the recognized controller medication class) for at least 3 months with a stable dose  $\geq 1$  month prior to Visit 1. Patients requiring a third controller are allowed to participate in this study. The third controller should also be used for at least 3 months with a stable dose  $\geq 1$  month prior to Visit 1 (patients requiring systemic steroids as controller medication or biologics are excluded). If patients take two different ICS, the total daily dose of ICS should be calculated to evaluate the eligibility criteria on daily dose of ICS which will be still considered as one controller. Please refer to medium and high dose of ICS in Appendix B. The minimum daily dose of fluticasone propionate is 500 mcg ( $\geq 250$  mcg of fluticasone propionate twice daily), which is equal to the upper limit of medium daily dose for fluticasone propionate as instructed in Appendix B. For ICS other than fluticasone propionate, please refer to the table in Appendix B which indicates the upper limit of the medium daily dose for each ICS which is equivalent to 500 mcg/day of fluticasone propionate.

If the Study Investigator based on his/her medical judgment, decides to optimize use of asthma medications prior to Visit 1 irrespective of potential participation in the study, note that changes in ongoing asthma medications must occur at least 1 month prior to Visit 1. The introduction of new controller medications must occur at least 3 months prior to Visit 1 with a stable dose for at least 1 month prior to Visit 1.

#### **8.2.1.2 Randomized treatment period**

During this period, patients will continue to take their controller medication(s) used during the screening period. The dose and regimen should not be changed. Only a transient increase in dose of ICS in addition to other rescue medication will be allowed to treat acute symptoms of asthma as per investigator's guidance. This will be recorded in the eDiary.

#### **8.2.1.3 Post-treatment period**

Upon completing the randomized treatment period, patients not continuing with the open label extension study will proceed to be treated with the controller medication regimen and dose used during the randomized treatment period, which could be adjusted based on the medical judgment of the investigator of the patients' asthma control status.

### **8.2.2 Reliever medication**

The reliever medication will not be dispensed or supplied by the sponsor.

Patients may administer albuterol/salbutamol or levalbuterol/levosalbutamol MDI as reliever medication as needed during the study. Nebulizer solutions may be used as an alternative delivery method.

The description of the criterion for qualifying an asthma exacerbation event based on nebulizer using, will use the nebulizer-to-puff conversion factor for application to loss of asthma control (LOAC) definition.

Study personnel should convert salbutamol/albuterol nebulizer and levosalbutamol/levalbuterol nebulizer use as shown on the following table:

Salbutamol/Albuterol Nebulizer Solution -Total Daily Dose (mg)	Number of Puffs*
2.5	4
5.0	8
7.5	12
10	16
*Conversion factor: salbutamol/albuterol nebulizer solution (2.5 mg) corresponds to 4 puffs	

- Example of salbutamol/albuterol Nebulizer-to-Puff Conversion: Patient received 3 salbutamol/albuterol nebulizer treatments (2.5 mg/treatment) between 7 and 11 AM. Total daily = 7.5 mg ->12 puffs

Levosalbutamol/Levalbuterol Nebulizer Solution -Total Daily Dose (mg)	Number of Puffs*
1.25	4
2.5	8
3.75	12
5	16
*Conversion factor: levosalbutamol/levalbuterol nebulizer solution (1.25 mg) corresponds to 4 puffs	

- Example of levosalbutamol/levalbuterol Nebulizer-to-Puff Conversion: Patient received 3 levosalbutamol/levalbuterol nebulizer treatments (1.25 mg/treatment) between 7 and 11 AM. Total daily = 3.75 mg ->12 puffs.

**Criterion used to specify an asthma exacerbation event in eCRF based on nebulizer use:**

After conversion of nebulizer-to-puff, in every instance that the number of puffs is  $\geq 6$  additional puffs of salbutamol/albuterol or levosalbutamol/levalbuterol in a 24-hour period (compared to baseline) on 2 consecutive days, tick the “Qualifying criteria box” on the asthma exacerbation event.

All other reliever medications rather than albuterol/salbutamol or levalbuterol/levosalbutamol should be avoided.

## **8.3 BLINDING PROCEDURES**

### **8.3.1 Methods of blinding**

Dupilumab and placebo will be provided in identically matched 2 mL or 1.14 mL pre-filled syringes. To protect the blind, each treatment kit of 2 mL (dupilumab / placebo) or 1.14 mL (dupilumab / placebo) glass pre-filled syringes will be prepared such that the treatments (dupilumab and its matching placebo according to its dose) are identical and indistinguishable and will be labeled with a treatment kit number. The randomized treatment kit number list will be generated by Sanofi.

Both the patient and investigator will be blinded to assigned active drug or placebo, but will not be blinded to the dose level of dupilumab 300 mg/matching placebo or dupilumab 200 mg/matching placebo due to different volume size (2 mL vs 1.14 mL).

Study patients, Investigators, and study site personnel will not have access to the randomization (treatment codes) except under circumstances described in Section 8.3.2.

### **8.3.2 Randomization code breaking during the study**

In case of an adverse event (AE), the code should only be broken in circumstances when knowledge of the IMP is required for treating the patient.

Code breaking can be performed at any time by using the proper module of the interactive voice response system (IVRS)/interactive web response system (IWRS) and/or by calling any other phone number provided by the Sponsor for that purpose. If the blind is broken, the Investigator should document the date, time of day and reason for code breaking.

Subject withdrawal will only occur when the code break call is made at the site level, not the study level. This means that if the Emergency Unblinding transaction is performed by the investigator (ie, at the site level), then the subject will be withdrawn from treatment. However, if the Emergency Unblinding transaction is performed by the Global Safety Officer (GSO) (ie, at the study level, as the GSO is not site based), then the subject will not be withdrawn from treatment.

At the facilities where the systemic drug concentration measurements, anti-drug antibodies and selected biomarkers are determined, the samples will be analyzed prior to data base lock leading to unblinding of responsible bioanalysts. Bioanalysts are excluded from the clinical trial team.

Patients, investigators and site personnel will not have access to assay results for immunoglobulins (IgG, IgG subclasses, IgA and IgM) after the first administration of study medication because these values have the potential for unblinding. Furthermore, neither patients, investigators nor site personnel will have access to eotaxin-3, antigen-specific IgE, total IgE, Eosinophil Cationic Protein (ECP), TARC or periostin while the study is ongoing, as the related data are not essential for patient care and have the potential for unblinding.

The Data Monitoring Committee will receive blinded by treatment group or unblinded (if necessary) confidential reports from an independent statistician for review, which have to be handled [REDACTED]. None of these reports can be delivered to unauthorized persons.

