#### 4.2.4 Rationale for dose and regimen selection

The dose regimens of subcutaneous (SC) dupilumab selected for this study are 300 mg every 2 weeks (q2w) or 200 mg q2w. Patients randomized to 300 mg q2w will get an initial loading dose of 600 mg on Day 1 while patients randomized to 200 mg q2w will get an initial loading dose of 400 mg on Day 1, and q2w dosing will commence 2 weeks after the loading dose. The administration of the loading dose of dupilumab will allow systemic concentrations to reach target saturation, potentially reducing the time to onset of clinical effect.

Proof of concept has been established in the ACT11457 study at 300 mg weekly. One hundred and four patients with persistent, moderate-to-severe asthma and a blood eosinophil count of at least 300 cells per microliter or a sputum eosinophil level of at least 3%, partially controlled or uncontrolled by medium-to-high doses of ICS plus LABA (fluticasone/salmeterol, budesonide/formoterol, or mometasone/formoterol) were randomized to the study. The study showed significant efficacy in a population of mostly severe asthmatics with poor asthma control and decreased lung function with mostly high doses of ICS in combination with a LABA.

In the dose ranging study (DRI12544 study), 776 patients with asthma uncontrolled by medium-to-high dose ICS plus LABA were randomized in the study. Four dose regimens (300 mg q2w with 600mg loading dose, 200 mg q2w with 400mg loading dose, 300mg q4w with 600 mg loading dose and 200mg q4w with 400 mg loading dose) were tested in the study. The results showed that 300 mg q2w and 200 mg q2w treatment with dupilumab provided a significant improvement on FEV1 at week 12 and a statistically significant reduction in the annualized rate of severe exacerbations when compared to placebo. Both dose regimens provided comparable efficacy on most of the efficacy endpoints regardless of the eosinophil count at baseline. Both doses were safe and well tolerated with a profile comparable to that seen with placebo except for an increased number of injection site reactions. To further characterize the optimal regimen for patients, both regimens will be assessed in the current trial.

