### 9.3.2 Pharmacodynamics

Several biomarkers related to asthmatic inflammation and Th2 polarization will be assessed for their value in predicting therapeutic response and/or in documenting the time course of drug response. In a prior asthma trial (ACT11457), treatment with dupilumab significantly suppressed systemic levels of serum TARC (CCL17; a ligand of CCR4 receptors that attracts Th2 cells), plasma eotaxin-3 (CCL26; a ligand of CCR3 receptors that attracts eosinophils and lung mast cells), and serum total IgE (a product of immunoglobulin class switching driven by IL-4), as well as reduced the concentrations of fractional exhaled nitric oxide (a marker of airway inflammation). Now added to these are the following serum biomarkers: eosinophil cationic protein (ECP; a stored protein released from activated eosinophils) and periostin, a protein reported to be elevated at baseline in patients responsive to treatment with anti-IL-13 antibodies.

Assay methodologies are briefly summarized below. More detailed information on the collection, handling, transport and preservation of samples (eg, minimum volumes required for blood collection and for aliquots for each biomarker assay) will be provided in a separate laboratory manual.

Eotaxin-3, eosinophil cationic protein (ECP), total IgE and Thymus and Activation-Regulated Chemokine (TARC) will all be assayed at the same time points as a biomarker set and as indicated in the study flow chart. Periostin and antigen-specific IgE panels will be collected individually per the study flow chart.

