#### **9.3.2.4 Exhaled nitric oxide**

Exhaled nitric oxide will be performed centrally and analyzed using a NIOX instrument (Aerocrine AB, Solna, Sweden), or similar analyzer using a flow rate of 50 mL/s, and reported in parts per billion (ppb). This assessment should be conducted prior to spirometry and following a fast of at least 1 hour. All exhaled nitric oxide recordings will be centrally read by independent experts. Further details on the procedure for measuring exhaled nitric oxide with NIOX will be provided in a separate instruction manual.

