2.1.7 Pharmacodynamics/genomics endpoints

Eotaxin-3, eosinophil cationic protein (ECP), total IgE and Thymus and Activation-Regulated Chemokine (TARC) will all be assayed at Visit 2(Week 0), Visit 8 (Week 12), Visit 11 (Week 24), Visit 14 (Week 36) and Visit 18(Week 52).

Periostin will be assayed at Visit 2(Week 0), Visit 4 (Week 4), Visit 8 (Week 12) and Visit 18(Week 52). And antigen-specific IgE panels will be collected at Visit 2(Week 0), Visit 8 (Week 12) and Visit 18(Week 52).

Blood eosinophil count will be measured as part of the standard 5-part WBC differential cell count on a hematology autoanalyzer.

Exhaled nitric oxide will be analyzed using a NIOX instrument (Aerocrine AB, Solna, Sweden), or similar analyzer using a flow rate of 50 mL/s, and reported in parts per billion (ppb). This assessment should be conducted prior to spirometry and following a fast of at least 1 hour at Visit 1(Week -4±1), Visit 2 (Week 0), Visit 3 (Week 2), Visit 4 (Week 4), Visit 8 (Week 12), Visit 9 (Week 16), Visit 10 (Week 20), Visit 11 (Week 24), Visit 14 (Week 36), Visit 17(Week 48), Visit 18(Week 52), Visit 19(Week 56), Visit 20(Week 60), Visit 21(Week 64)

Pharmacogenetic testing is optional and voluntary. A separate written informed consent form must be signed before sampling. For those patients who signed the optional pharmacogenetic informed consent form, blood samples for exploratory genetic analysis of DNA or RNA will be collected at the study visit as specified in the study flow chart, and these samples will be stored for future analysis.

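### FeNO is missing from the results withheld from sites and patients, and neither document says that its post-dose values are masked

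*Protocol*

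**What the plan says.** Protocol Section 8.3.2 withholds post-dose immunoglobulin results and then states that no patient, investigator or member of site staff "will have access to eotaxin-3, antigen-specific IgE, total IgE, Eosinophil Cationic Protein (ECP), TARC or periostin while the study is ongoing". It gives two reasons: "as the related data are not essential for patient care and have the potential for unblinding". FeNO is not named.

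Protocol Section 9.3.2 reports that in the earlier asthma trial (ACT11457) dupilumab suppressed TARC, eotaxin-3 and total IgE and also "reduced the concentrations of fractional exhaled nitric oxide (a marker of airway inflammation"). Section 4.2.4 gives the regimen of that trial: "Proof of concept has been established in the ACT11457 study at 300 mg weekly".

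On handling, Protocol Section 9.3.2.4 says "Exhaled nitric oxide will be performed centrally and analyzed using a NIOX instrument" or a similar analyser, that the test comes before spirometry, and that "All exhaled nitric oxide recordings will be centrally read by independent experts". It leaves the procedure to a separate instruction manual. SAP Section 2.1.7 schedules readings at Visits 1 and 2 and then at "Visit 3 (Week 2), Visit 4 (Week 4), Visit 8 (Week 12), Visit 9 (Week 16), Visit 10 (Week 20), Visit 11 (Week 24"), followed by Weeks 36, 48 and 52 and the three post-treatment visits.

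**The concern.** Section 8.3.2 is where the protocol specifies which results are masked. It applies its reasoning to six markers and leaves out one that the protocol itself reports as responsive to the drug. The others are assays on blood samples. FeNO is measured in the course of the site visit, with two pre-dose readings available as a within-patient reference.

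Syringe volume already discloses the dose level (Section 8.3.1), so active versus placebo within a volume is all that the blind still conceals. If sites or patients could see FeNO fall, that concealment would be weakened. A severe exacerbation is defined by systemic corticosteroid use for at least three days, or by a hospital or emergency visit requiring it (Section 9.1.1.1), and exacerbations are managed on the investigator's judgment (Section 10.4.1.1). This endpoint is the first test in the hierarchy. Loss-of-asthma-control events can also be triggered by increases in inhaled steroid, which follow the investigator's guidance (Section 8.2.1.2).

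**Working it through.** The plan states no figure on this point. The check compares sections.

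**1. Drug effect against masking**

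| Marker | Section 9.3.2 reports lowering by dupilumab | Withheld in Section 8.3.2 |
|---|---|---|
| TARC | yes | yes |
| Eotaxin-3 | yes | yes |
| Total IgE | yes | yes |
| FeNO | yes | **no** |
| ECP | no effect reported | yes |
| Periostin | no effect reported | yes |
| Antigen-specific IgE | no effect reported | yes |

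Three of the four markers reported as lowered are withheld; FeNO is the exception. Three markers with no reported effect are withheld as well.

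**2. Need for the value at the site.** No inclusion or exclusion criterion (Sections 7.1 and 7.2), discontinuation rule (Sections 10.3.1 and 10.3.3) or safety instruction (Section 10.6) uses FeNO.

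**3. Number of readings.** Post-dose readings up to Week 52 fall at Weeks 2, 4, 12, 16, 20, 24, 36, 48 and 52, which is nine for a patient who completes treatment. The ninth comes at the end of the exacerbation period, so at most eight could influence earlier decisions. Two (Weeks 2 and 4) come from visits before Week 12; the Week 12 reading is taken shortly before that day's spirometry.

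**4. Whether central reading implies masking.** Section 9.2.1.1.1 uses matching language for spirometry. Sites must see those results: they verify FEV1 eligibility at Visits 1 and 2 (Sections 10.1.1 and 10.1.2), and clinic staff score FEV1 % predicted for the ACQ-7 (Section 9.2.1.1.3.1). The phrase therefore does not establish that FeNO is hidden. It does not establish that FeNO is shown either.

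**5. What would have to be assumed to give a size.** The inputs below marked as assumed are not in the documents. The results are not estimates for this trial.

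- *Guessing.* Allocation within a volume is 2:1, so always guessing active is right 2/3 = 66.7% of the time. Assume normal FeNO changes separated by d standard deviations, one reading, and the best cut-off t = d/2 − ln(2)/d. Then the proportion correct is (2/3)[1 − Φ(t − d)] + (1/3)Φ(t). For d = 0.5, 1.0 and 1.5 this gives 67.5%, 73.0% and 79.6%.
- *Consequence.* Use a Wald test on the log rate ratio, with variance (1/rate + dispersion)/n in each arm. With the plan's inputs (0.6 versus 0.27, dispersion 2, 273 versus 546) it gives 99.9% power against the stated 99%, and in the high-eosinophil subgroup (115 versus 230) 91.8% against 91%. Now assume a true ratio of 1 and a net fraction b fewer events recorded on active. For b = 0.10 the standard error is √[(1/0.6 + 2)/273 + (1/0.54 + 2)/546] = 0.143, and |ln 0.9|/0.143 = 0.74. The rejection probability is then about 11.4% instead of 5%. For b = 0.05, 0.15 and 0.20 it is 6.5%, 20.4% and 33.9%.

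The documents give neither d nor b, and nothing links one to the other.

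**The case against.** The strongest reply is that visibility is not documented. Neither document says that sites or patients see the FeNO value, and the separate manual may already mask it. That stands. A reader might infer from the omission that the blind is broken or that results will be biased; the documents support only that masking is not stated.

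The effect is also borrowed. It was seen at 300 mg weekly, in a trial of 104 patients selected for raised blood or sputum eosinophils (Section 4.2.4). This trial doses every two weeks and also enrols patients below 300 cells/µL. With no effect size or within-patient variability given, the strength of any unblinding is unknown. That stands too, and it rules out quoting a biased rate ratio.

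A reader might also suppose that all efficacy endpoints are equally open to influence. They are not. Section 10.1 recommends completing questionnaires before FeNO at each visit, so only earlier readings could colour them, and spirometry is read centrally by independent experts. The severe exacerbation definition sets a minimum duration of steroid use or requires hospital or emergency care, which limits discretion without removing it.

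Finally, the protocol never declares FeNO unnecessary for care, as it does for the listed assays. That is true, but no section requires sites to use it, so this is a weak reason for leaving it visible.

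**Conclusion.** The gap is real and worth closing. By the protocol's own account FeNO belongs with markers that it withholds as potentially unblinding, and neither document masks it. The consequence is conditional: if post-dose values are visible, sites or patients could infer active versus placebo. The principal exposure would be severe exacerbations and loss-of-asthma-control events that turn on investigators' decisions about systemic or inhaled steroids. FEV1 and questionnaires from the same visit are less exposed.

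No size can be put on the bias from the documents. The conclusion rests on Sections 8.3.2 and 9.3.2 read together and on the absence of any masking statement; it does not rest on the assumed figures above.

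**What to change.** In Protocol Section 8.3.2, add FeNO values obtained after the first dose to the results not available to patients, investigators and site personnel while the study is ongoing. Set the analyser or vendor portal to hide post-randomization values. If the instruction manual already does this, state it in Section 8.3.2.

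The cost is one sentence and a device or portal setting. The measurements are still taken and centrally read, so no planned biomarker analysis is lost, and the SAP's baseline FeNO subgroup is unaffected. The small downside is that sites cannot draw on study FeNO readings for care, a use that no section requires.
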